community fitness and will be inclusive of all individuals with chronic health conditions. Physical activity and exercise guidelines recommend everyone, including those with chronic health conditions, strive for 150 minutes of moderate intensity aerobic exercise per week.¹ This study will contribute to the knowledge of how patients achieve recommended individual HR and moderate-high intensity zones during exercise.

Aim 1: Measure the extent to which monitoring and education regarding intensity is provided (1) before HR monitoring intervention, (2) when providers know HR monitoring is occurring but without visual feedback, and (3) with visual feedback of HR monitoring.

We hypothesize providers will modify their behavior in the number of times they ask about intensity, adjust session intensity or provide education regarding intensity when visual feedback is provided compared to no feedback, which will be further increased from pre-study baseline levels.

Aim 2: Determine the efficacy of using HR with visual feedback during rehabilitation to reach target intensity.

We hypothesize participants will have higher mean HR and increased time in their individualized target HR zones when given visual feedback compared to no feedback during group sessions.

Aim 3: Determine the safety of using Heart Zones technology in rehabilitation for increasing participant exercise intensity.

We hypothesize the technology will be safe without an increase in number of adverse events throughout their rehabilitation stay.

Aim 4: Assess patient acceptability, exercise self-efficacy and confidence following use of Heart Zones technology in rehabilitation sessions.

We hypothesize use of Heart Zones technology in group settings with feedback will increase participant self-efficacy and confidence in reaching higher exercise intensities, and will be well accepted. Furthermore, we hypothesize the use of Heart Zones will be feasible in at least 75% of patient's group sessions.

Aim 5: Explore the feasibility of submax exercise testing when completed 2 times to establish individualized training targets for individuals receiving inpatient rehabilitation.

We hypothesize submax exercise testing will be feasible to perform, safe and informative to clinicians to establishing individualized heart rate zones. We believe there will be a change pre to post in submax testing indicating improvement in patient's condition.

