Clinical providers have many options for submaximal (submax) aerobic capacity testing, although they are rarely used outside of cardiac rehabilitation. The 6 minute walk test which have been studied in a range of populations including heart failure, end stage lung disease, COPD, chronic renal failure, and older individuals.¹⁵ The recumbent stepper test has been shown to be able to predict VO₂ peak in healthy adults.¹⁶ For individuals with limited ambulatory or lower extremity motor function, an alternative to determine aerobic capacity is to use the arm crank ergometer.¹⁷

This study will facilitate the understanding of feasibility and safety of moderate to vigorous aerobic endurance exercise, based on individually set aerobic intensity zones carried out in a rehabilitation setting. It will also study if the behavior of the provider or participant changes when provided visual feedback of HR during sessions.

STUDY ENDPOINTS:

[figure not shown]
- To evaluate the safety of using Heart Zones technology in a rehabilitation model across the rehabilitation continuum by recording the incidence of adverse events.
- To demonstrate the feasibility of using Heart Zones during group sessions by measuring the incidence of session usage to missed sessions.
- To demonstrate the efficacy of using visual feedback of HR monitoring to achieve greater intensities during sessions compared to no visual feedback of HR.
- To analyze the effect of HR monitoring with visual feedback on therapist perception of acceptability, feasibility and appropriateness as well as participant exercise self-efficacy and confidence.
- To assess feasibility of submax exercise testing in the inpatient setting to establish individualized target training intensities and assess the change in submax testing when completed at 2 times points.

STUDY INTERVENTION(S) / INVESTIGATIONAL AGENT(S):

Heart Zones is a commercially available software platform that integrates feedback from several different commercially available HR sensors. The software platform displays HR and provides continuous biofeedback with ability to provide individualized programs to maximize individual and multi-person sustained effort. It has the capability to record session data for later review and analysis.

We are not evaluating safety or effectiveness of the Heart Zones software, rather assessing the effect of monitoring HR with visual feedback in a group setting.

STU#: 00216223

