We will be using commercially available non-invasive, wireless HR monitors, such as the Scosche forearm monitor or other monitors with Bluetooth capability to pair with the Heart Zones platform. Scosche has a sensor with Velcro strap armband that is able to be cleaned with standard hospital cleaning procedures (Cavicide) between patient uses, yet is affordable, accessible and easy to use. Multiple heartrate monitors can be paired simultaneously and paired with a display such as an Apple IPad or other screen. Through visual display of multiple HRs in real time, it is feasible to use the Heart Zones application during a group rehabilitation session. The display monitors, HR monitors and Heart Zones platform will be stored in a locked cabinet accessible to research personnel for authorized use with this study.

PROCEDURES INVOLVED:

AIM1:

This will be conducted prior to enrollment of subjects into active phases of the study in order to understand baseline provider behavior regarding education to patients regarding intensity, monitoring of intensity and progression/modification of session intensity.

Observation of 15 sessions of each of the following conditions (total of 1500 minutes/condition):

1. Condition 1: Baseline Provider Behavior (prior to study beginning)
2. Condition 2: HR monitor on, no visual feedback
3. Condition 3: HR monitor on, visual feedback

Record number of instances in session the following occur:

- Provider provides education regarding HR/RPE/intensity
- Provider monitors HR/vitals
- Provider ask for RPE from patient
- Provider mentions target RPE/HR range
- Provider modifies task to reach target RPE/HR range

AIMS 2-5:

Screening Procedures & Consent

1. Potential subjects will be recruited from multiple settings across the continuum of rehabilitation as they are admitted.

STU#: 00216223

2. Once informed consent is obtained, screening will be performed to ensure inclusion criteria for study are met
3. Medical clearance for participation from supervising physician through online REDCap form.

2. Baseline

1. Participants will complete submax exercise test with licensed physical therapist in order to establish individualized HR intensities and zones.
 - i. Based on participant capability and timing, we will perform one or more of the submax tests or HR zone calculation methods for the individual based on clinical presentation and functional capacity.

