1. At the end of the study, we will ask participants to answer one summative quality improvement question regarding their participation in the study.
 - i. If discharged unexpectedly, we will attempt to reach out to participants via their preferred contact method (phone or email) in order to allow them to provide feedback.
2. We will collect information from their electronic medical record including new medical complications or concerns, their current functional level based on QI mobility items and outcome measures completed and ask the participant regarding discharge destination.
3. If the submax exercise test was completed at baseline, we will complete the same test a second time at least 3 days later.

AIM 6:

- a. We will ask for provider feedback and perceptions at the end of the study by their completion of the Acceptability, Appropriateness and Feasibility Questionnaire.
- b. Given the potential for covering providers, we will only ask participation from participating providers who are core staff/covering for a long term placement at each of the study locations.

STU#: 00216223

SHARING RESULTS WITH PARTICIPANTS

Given the nature of the study design, participants will receive immediate continuous feedback of their heartrate for a portion of the study. Individual study results may be provided once the study is completed if the patient requests. Results will be shared in written or verbal means, depending on participant's preference.

STUDY TIMELINES

The participant will be in the study for up to the duration of their length of stay in inpatient rehabilitation or day rehabilitation. We anticipate that it will take up to 8 months to enroll all study participants and primary analyses will be completed by September 2022.

INCLUSION AND EXCLUSION CRITERIA

Participant Criteria:

Inclusion:

- Age 18-90 years
- Admitted to inpatient rehabilitation, day rehabilitation or participant in community fitness
- Qualifies for group therapy based on diagnosis and insurance reimbursement
- Physician clearance for participation

Exclusion:

- Unable to provide informed consent due to cognitive impairment
- Inability to communicate with investigators
- Sternal Precautions
- Individuals with LVADs
- Pregnant women
- Uncontrolled Hypertension
- Serious and unstable cardiac arrhythmias
- Loss of bilateral upper extremity sensation
- At high risk for skin breakdown due to poor skin integrity (open wound, fragile skin, etc)

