- Risk of loss of confidentiality will be minimized by not including personal identifying information on forms (participant will be assigned a research study number) and by conducting data collection in a private setting.

POTENTIAL BENEFITS TO PARTICIPANTS

There is likely no direct benefit to participants. Participation in this study will help researchers understanding if the use of visual feedback of HR in a group setting is feasible, efficacious and acceptable as care provided in a group model is a standard in rehabilitation.

DATA MANAGEMENT AND CONFIDENTIALITY

The analytic plan follows from the aims and the hypotheses. Descriptive statistics will be used to describe the participants and the data. Statistical tests will be utilized to assess for differences in individual outcomes baseline, mid and post through paired t-tests or appropriate non-parametric tests in consultation with a statistician. Data regarding the aims below may be analyzed for group sessions, individual sessions, and combined.

Aim 1: The null hypothesis is that there is no different in therapist behaviors to monitor/progress intensity prior to study, without visual feedback, or with visual feedback of participant's HR.

Aim 2: The null hypothesis is that there will be no difference in participant's ability to reach target intensity between sessions in which visual feedback of HR is provided and sessions where there is no visual feedback.

Aim 3: The null hypothesis is that there will be no increase in number of adverse events related to the use of Heart Zones with and without visual feedback.

Aim 4: The null hypothesis is that there will be no difference in participant exercise self-efficacy and confidence in reaching appropriate intensity when using visual feedback to no visual feedback during sessions.

Aim 5: The null hypothesis is that there will be no difference between submax exercise tests completed at baseline compared to post.

STU#: 00216223

Aim 6: The null hypothesis is that the providers will not feel the technology is appropriate, acceptable or feasible to use in a rehabilitation setting.

Data will be transferred to and stored on Shirley Ryan AbilityLab's REDCap system.

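### Aim 5 asks whether repeat submaximal testing is feasible in inpatients, but its only aim-specific analysis is a paired test in completers, which cannot show feasibility and does not by itself establish improvement

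*Combined protocol and SAP*

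**What the plan says.** The Objectives section states Aim 5 as "Explore the feasibility of submax exercise testing when completed 2 times to establish individualized training targets for individuals receiving inpatient rehabilitation". The hypothesis beneath it has two parts. The first is "We hypothesize submax exercise testing will be feasible to perform, safe and informative to clinicians". The second is that "there will be a change pre to post in submax testing indicating improvement" in the patient's condition. Study Endpoints likewise lists "To assess feasibility of submax exercise testing in the inpatient setting" together with the change between two time points.

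Under Procedures Involved, Aims 2-5, the Baseline step says "we will perform one or more of the submax tests or HR zone calculation methods", chosen by clinical presentation, functional capacity and timing. The list that follows includes a heart-rate-reserve formula that can stand in for a formal test, zones set by clinical discretion, and three exercise tests: the 6-minute walk, the seated stepper and the arm crank. The Post step says: "If the submax exercise test was completed at baseline, we will complete the same test a second time at least 3 days later".

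The analysis plan sits under Data Management and Confidentiality. It promises descriptive statistics in general, and paired t-tests or non-parametric equivalents for individual outcomes. Its Aim 5 entry is a single null hypothesis, that "there will be no difference between submax exercise tests completed at baseline compared to post".

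**The concern.** The aim is about whether testing can be done; the analysis is about whether scores move among those in whom it was done. If the plan is followed as written, a named aim and endpoint could be reported through a p-value that carries no information on completion. The bypass routes at baseline make this more than a formality, because how often the test is replaced, and why, is the substance of a feasibility result.

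There are two further problems. The plan does not name the variable to be compared, although the three tests produce different quantities. It also intends to read a change as improvement in the patient's condition, with no comparison group to separate true change from the effect of repeating a test.

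**Working it through.** **No plan figure to reproduce.** The stated sample size is 90 to complete, from at most 120 consented (Participant Populations). It covers inpatient, day rehabilitation and community fitness together. No inpatient number, alpha, power, effect size or SD is given, and nothing is specific to Aim 5. The figures below are therefore illustrations on stated assumptions.

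**Step 1: match the aim to the analysis.**

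| Element of Aim 5 | Measure or analysis specified |
|---|---|
| Feasible to test twice in inpatients | No numerator, denominator or criterion |
| Safe, informative to clinicians | No measure specific to submaximal testing |
| Change from baseline to post | Paired test of no difference; variable and direction not named |

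By contrast, the plan does define feasibility for Heart Zones: session usage against missed sessions (Study Endpoints), with a 75% criterion (Aim 4).

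**Step 2: what a paired test can say about completion.** The paired t statistic is mean(d) / (SD(d)/√n), where n is the number of completed pairs. The number of inpatients enrolled, N, does not enter. Take n = 30 (assumed) and vary N (assumed). The completion proportion is n/N, with its exact (Clopper-Pearson) 95% confidence interval:

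| N enrolled | Completion of both tests | Exact 95% CI |
|---|---|---|
| 30 | 30/30 = 100% | 88% to 100% |
| 45 | 30/45 = 67% | 51% to 80% |
| 60 | 30/60 = 50% | 37% to 63% |
| 90 | 30/90 = 33% | 24% to 44% |

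The paired test is identical in all four rows.

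**Step 3: what is being compared.** As described under Baseline, the walk yields distance and an estimate of peak VO2, the stepper yields heart rate and wattage by stage, and the arm crank seeks a steady-state heart rate at a load held constant after the first 3 minutes. A longer walk is a better result, whereas a lower heart rate at the same load is usually the better result. Without a named variable and direction for each test, rejecting the null does not say which way patients moved.

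**Step 4: how easily a retest shift reaches significance.** Suppose familiarity with the test alone shifts scores by a fraction δ of the SD of the paired change. The rejection probability of a two-sided 5% paired t-test comes from the noncentral t distribution with n − 1 degrees of freedom and noncentrality δ√n. For example, with n = 30 and δ = 0.3 the noncentrality is 0.3 × 5.48 = 1.64, the critical value is 2.05 and the probability is 0.355.

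| Completed pairs | δ = 0.2 | δ = 0.3 | δ = 0.5 |
|---|---|---|---|
| 24 | 16% | 29% | 65% |
| 30 | 18% | 36% | 75% |
| 36 | 21% | 42% | 83% |
| 45 | 26% | 50% | 91% |

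The pair counts 24 and 36 correspond to 45 enrolled inpatients with 40% or 10% never tested and 90% of those tested completing both: 45 × 0.6 × 0.9 = 24.3 and 45 × 0.9 × 0.9 = 36.5, rounded down. The row for 45 has every one of them contributing a pair. All of these rates are assumed.

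**The case against.** The strongest reply is that Aim 5 is exploratory. Feasibility is already listed as an endpoint, and a completion count is a descriptive statistic that needs no null hypothesis; the plan promises descriptive statistics and says that its analyses follow from the aims. This stands in part. The plan does not rule out a completion count, so it would be too strong to say that feasibility can never be reported under it. But that sentence fixes no numerator, no denominator and no handling of people whose test was replaced. The result could be given as a proportion of those tested or of all enrolled, with very different values.

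Three stronger readings are tempting, and the documents do not support them.

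- **That people given a formula or discretionary zone leave the study data.** Nothing says so. They are absent from the paired comparison only, because they have no test to repeat.
- **That the three tests will be pooled into one comparison.** The plan does not say this. The same test is repeated within a person, so each pair is like with like, and estimated aerobic capacity could serve as a common scale. The defect is that the outcome is unnamed.
- **That the plan claims an effect of training or of visual feedback on test scores.** It claims improvement in the patient's condition, and natural recovery is such an improvement. Random measurement error is also allowed for by the paired test. What remains is practice, regression to the mean and selection of those able to repeat the test.

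The 3-day interval is a minimum. The retest belongs to the Post step and inpatients are scheduled for two weeks, so many intervals may be longer. No upper limit is set.

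**Conclusion.** The point holds in this form. The one analysis specific to Aim 5 cannot answer the question that the aim asks, and the general descriptive sentence does not define what would. On the assumed enrolments, the same 30 pairs are compatible with completion anywhere from 33% to 100%.

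The planned reading of change is also unsupported as it stands. An assumed practice shift of 0.3 SD would be significant about 29% of the time with 24 pairs, 36% with 30, 42% with 36 and 50% with 45. Those figures depend on the assumed shift and on a number of inpatients that the plan does not state. The figure of 90 should not be used as an inpatient count, because it is the target for all settings. The mismatch between aim and analysis depends on none of these assumptions.

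This should be changed, but it is confined to one exploratory aim and does not affect the comparison of feedback with no feedback.

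**What to change.** 1. Make feasibility the main Aim 5 estimate. Report, among all enrolled inpatients, the proportion who complete a baseline submaximal test and the proportion who complete both tests, each with an exact 95% confidence interval.
2. Count as not tested only those who had no submaximal test. Someone given a formula in addition to a test counts as tested. Record the reason whenever no test, or no second test, was done.
3. Report pre-post change separately by test type, with one named outcome and direction per test (or estimated peak VO2 where the test gives it), its confidence interval and the days between tests.
4. In the Aim 5 hypothesis and analysis entry, describe the change as uncontrolled and do not state that it indicates improvement.

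The cost is wording in two places and one reason-not-tested field, which should be in place before enrolment because reasons may not be recoverable later. No patients, visits or tests are added. Splitting by test type leaves fewer pairs per test and so wider intervals, which reflect the information actually available.
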